## ***Random allocation procedure***

Patients will be randomly assigned to one of the three treatment groups with an equal probability of assignment to each treatment (allocation ratio 1:1:1). The study biostatistician will prepare the sequence of treatments according to a randomized permuted blocks procedure and the randomized list will be centralized. The randomization list will be generated using SAS 9.4 release. The randomised allocation of treatment ID will be centralised.

Upon recruitment of a patient meeting the inclusion criteria, the local investigator will follow an online procedure (detailed in the Manual of Procedures) to know the treatment ID of the patient. After randomization the treatment ID, along with patient's weight and patient code, will be transmitted to the hospital pharmacist who is in charge to prepare the study treatment according to randomization arm.

## ***Blinding procedure***

Ivermectin and placebo treatment will be double blinded, i.e. the treatment will be unknown to both the subject and the treating physician. The hospital pharmacist will be unblinded to study treatment because in charge to prepare the study treatment according to randomization arm.

The study medication will be labeled using a unique treatment ID, which is linked to the patient code. For each patient the treatment ID assigned at the time of randomization will be the same during the whole treatment period. The active and placebo kits will be presented in the same packaging to ensure blinding of the study medication.

The Investigator will receive sealed emergency envelopes allocated to his/her site. Each envelope is labeled with the protocol acronym and a treatment ID. Inside the envelope, the respective treatment arm is recorded. The Investigator is authorized to unseal the envelope only in case of a medical emergency when adequate treatment of the concerned patient requires immediate knowledge of the actual previous trial treatment.

If felt useful, the investigator may first discuss options with the other investigators and the scientific coordinator from Sponsor before unblinding the subject's treatment assignment.

Situations other than medical emergencies may require unblinding of a subject's treatment assignment. In these cases, a discussion with the Principal Investigator and with the Sponsor staff is recommended before the patient is unblinded.

If this is impractical, the investigator must notify to the Sponsor as soon as possible, but without revealing the treatment assignment of the unblinded subject, unless that information is important for the safety of subjects currently in the study.

Specific procedures for emergency unblinding of a subject's treatment are provided in the appropriate "Unblinding procedures".

The study pharmacovigilance dedicated staff retains the right to break the code for SAEs that are unexpected and are suspected to be causally related to the investigational product and that potentially require expedited reporting to regulatory authorities. The subject who has been unblinded may continue on study treatment according to clinical judgement.

In case of code break, the Investigator must complete the "Unblinding Form" providing the date of and reason for unblinding and send it to the Sponsor and the Safety Desk of the Sponsor immediately and no later than 24 hours from the time of unblinding via email to the Sponsor ([[contact]](mailto:[contact])) and the study safety desk ([[contact]](mailto:[contact])), respectively. Thereafter, the Investigator should access the Electronic Data Capture (EDC) system as soon as possible and report this information in the electronic Case Report Form (eCRF). During each monitoring visit, the monitor will check whether the emergency envelopes are still intact.

## ***Statistical Analysis***

Data will be analyzed by the study biostatistician using the software SAS 9.4 release. A full Statistical Analysis Plan will be written prior to statistical analysis.

The primary safety analysis will be performed on safety analysis set, including patients who received at least one dose of study treatment.

The analysis of primary efficacy as well as secondary outcomes will be performed according to an Intention to Treat basis (ITT) considering all subject as originally assigned to the treatment arms.

Patients with missing values and patients lost during treatment or at follow-up will contribute to the analysis of the secondary outcomes only for the time during which data are available. A per-protocol (PP) analysis will be also performed including only patients who took the allocated treatment as specified in the protocol, in order to check for consistency with the primary analysis.

## **Analysis of the primary outcome**

The proportion of patients in each experimental group experiencing at least one SADR will be described by means of frequency and percentages.

The mean of the differences in viral load decline from baseline to 7 days between each experimental group and the control group will be described by standard summary measures for continuous data and compared by mean of Student T test or the equivalent non parametric method (according to the Barlett's test for homogeneity of variances).

### **Analysis of the secondary outcomes**

Binary outcomes will be described by frequencies and proportions and summarised by mean of absolute and relative difference, with their relative 95% CI. Mantel Haenzel test will be used for pairwise comparison between groups. For expectedly rarer outcomes (such as deaths, patients with blood test alterations during treatment), Fisher's exact test will be used if required.

Continuous variables will be first assessed with Barlett's test for homogeneity of variances. Then, the t-test for comparing two means or the Wilcoxon rank sum for non-normal populations, whichever the more appropriate, will be used.

The pattern of compliance to treatment will be explored and compliers/non compliers will be compared with respect to baseline demographic and clinical data.

Time to clinical resolution (TCR) will be calculated as the time from randomisation to clinical resolution or death. A competing risk model will be used to analyze TCR, since the death is considered as competing event.

The assessment of safety profile will be mainly based on adverse reactions (ARs) and the frequency and nature of SAEs.

For each patient and for each type of adverse event, the worst degree ever suffered during treatment will be used for the analysis. All safety parameters will be presented and analyzed in terms of listings and summary tables.

The proportion of patients in each group experiencing adverse events will be compared through the chi-square test (or the Fisher's exact test when appropriate).

SAEs will be summarized by presenting the number and percentage of patients having any SAE. Other information collected (e.g. severity or suspected relationship to study medication) will be listed as appropriate.

Generalized longitudinal mixed models will be used to analyze the trend over time of viral load at different time points (baseline, 7 days, 14 days, 30 days).

Multiple regression will be used to study the variation of main random variables according to several potential predictor variables including among others: age; sex; continent of origin; recruiting centre; test results on recruitment.

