## **STUDY DESIGN**

This is a multicentre, prospective, randomized, double-blind, adaptive phase II dose finding study.

Patients meeting the inclusion criteria will be asked to participate to the study and randomized in a 1:1:1 ratio to either:

- Placebo arm (arm A): placebo will be identical in appearance to ivermectin in order to preserve blinding and will be administered p.o. at empty stomach with water once daily, for 5 days

- Intervention arms: a) Ivermectin, single dose 600 µg/kg, for 5 days (I\_600) and placebo (arm B) ; b) Ivermectin, single dose 1200 µg/kg, for 5 days (I\_1200) (arm C) ); these drugs will be administered p.o. once daily, for 5 days.

In arm A and B, the number of placebo tablets to be administered will be calculated by the study dedicated pharmacist considering the number of tablets that should be taken in case a patient with the same weight is assigned to arm C.

[figure not shown]
Patients will be randomized by a centralized computer system. At randomization a treatment ID is assigned to the patient. Once a treatment ID is assigned this must not be re-assigned even in cases of errors.

Enrolled subjects will be identified by a unique subject number (patient code) that will remain consistent for the duration of the study.

Patients will be recruited at the emergency room of hospitals, and/or among asymptomatic hospital workers found positive for SARS-CoV-2 at routine screening and/or in outpatient ambulatory settings, and/or at home, if not meeting the clinical criteria for hospitalization, according to the routine procedure of each participating site. The expected duration of subjects inclusion in the study is of 3 months, or until the planned number of subjects to be enrolled will be reached.

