**Table 3 Standard definitions of safety events**

Adverse Event (AE)	Any untoward medical occurrence in a participant to whom a medicinal product has been administered, including occurrences which are not necessarily caused by or related to that product.
Adverse Reaction (AR)	
An untoward and unintended response in a participant to an investigational medicinal product which is related to any dose administered to that participant.
 
The phrase "response to an investigational medicinal product" means that a causal relationship between a trial medication and an AE is at least a reasonable possibility, i.e. the relationship cannot be ruled out.
 
All cases judged by either the reporting medically qualified professional or the Sponsor as having a reasonable

	
suspected causal relationship to the trial medication qualify as adverse reactions.

Serious Adverse Event (SAE)
	
A serious adverse event is any untoward medical occurrence that:
 
 
- results in death
 
- is life-threatening
 
- requires inpatient hospitalisation or prolongation of existing hospitalisation
 
- results in persistent or significant disability/incapacity
 
- consists of a congenital anomaly or birth defect.
 
 
Other 'important medical events' may also be considered serious if they jeopardise the participant or require an intervention to prevent one of the above consequences.
 
NOTE: The term "life-threatening" in the definition of "serious" refers to an event in which the participant was at risk of death at the time of the event; it does not refer to an event which hypothetically might have caused death if it were more severe.

Serious Adverse Reaction (SAR)
	
An adverse event that is both serious and, in the opinion of the reporting Investigator, believed with reasonable probability to be due to one of the trial treatments, based on the information provided.

Suspected Unexpected Serious Adverse Reaction (SUSAR)
	
A serious adverse reaction, the nature or severity of which is not consistent with the Reference Safety Information for the medicinal product.
 
The RSI for ivermectine/placebo is contained in the Summary of product characteristics ('SmPC').

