### **SAE**

To ensure patient safety, every SAE, regardless of suspected causality, occurring from the acquisition of the informed consent until the date of last visit must be immediately reported to Sponsor and always within 24 hours of learning of its occurrence.

The investigator will notify the Study safety desk all SAEs occurring during the treatment period.

To notify the Sponsor, the identified SAEs should be recorded and described on the appropriate SAE form of the eCRF, which should be dated and signed electronically. By clicking on a specific link in the form, an automatic email will be sent to Study Safety Desk and to all Investigators with EDC system access.

In case the EDC system is malfunctioning, the SAE should be notified by completing an editable pdf SAE form provided during the site activation and sending it by email or fax within 24 hours of the initial observation of the event to the Study safety desk:

Laboratory of Methodology for Clinical Research

Istituto di Ricerche Farmacologiche Mario Negri IRCCS

Study Safety Desk

email: [[contact]](mailto:[contact])

Fax: [name]

Once EDC system functionality is restored, all the cases reported through the pdf SAE form must be entered in the electronic SAE form of the EDC system.

Any new or additional information regarding the SAE must be reported as follow-up to the original episode within 24 hours of the investigator receiving the follow-up information. Once

a SAE is detected, it should be followed until its resolution or until it is judged to be permanent. Follow-up information is sent to the same contact(s) to whom the original SAE report form was sent, using a new SAE report form stating that this is a follow-up to the previously reported SAE.

The repetition of the same SAE after its resolution should be reported as a second separate event.

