### ***Study recording period and follow-up for adverse events and serious adverse events***

Adverse events and serious adverse events will be recorded from time of acquisition of informed consent, throughout the treatment period and including the safety follow-up period (25 days after the last study drug administration). During the course of the study all AEs and SAEs should be proactively followed up for each participant. Every effort should be made to obtain a resolution for all events, even if the events continue after discontinuation/study completion.

The investigator is responsible for following all SAEs until resolution, until the participant returns to baseline status, or until the condition has stabilized with the expectation that it will remain chronic, even if this extends beyond study participation.

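### AE grades are analysed only during the five treatment days although AEs are recorded to 25 days after the last dose, and the causality test behind the Step 1 SADR endpoint is stated inconsistently

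*Protocol*

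**What the plan says.** **Grading window.** Under Analysis of the secondary outcomes, for each patient and type of adverse event, "the worst degree ever suffered during treatment will be used for the analysis". Study Design gives the length of treatment: "these drugs will be administered p.o. once daily, for 5 days". The section on the recording period has AEs and SAEs recorded from consent, "throughout the treatment period and including the safety follow-up period (25 days after the last study drug administration". Routine visits requires a blood count and ALT at Days 7 and 14. Table 1 marks blood monitoring at baseline, Day 7, Day 14, unscheduled visits and Day 30, and leaves Days 1 to 5 blank.

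**Primary safety endpoint.** Step 1 takes the occurrence of a SADR as its endpoint and refers to the adverse event section for definitions. An arm passes with 4 or fewer SADRs in 20 patients and is closed with 5 or more. The abbreviation list expands SADR, but the definitions section has entries only for AE, adverse (drug) reaction, serious adverse event or reaction, and SUSAR.

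**Causality.** In Table 3, the adverse reaction row says that the causal link "is at least a reasonable possibility, i.e. the relationship cannot be ruled out", and accepts the view of either the reporting professional or the Sponsor. The serious adverse reaction row requires the event to be "believed with reasonable probability to be due to one of the trial treatments", in the reporting investigator's opinion. The section Relationship to study agents gives sites one test for AEs and SAEs alike, and it is the lower one, reasonable possibility.

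**SAE reporting.** Every SAE "occurring from the acquisition of the informed consent until the date of last visit must be immediately reported to Sponsor". The next paragraph reads: "The investigator will notify the Study safety desk all SAEs occurring during the treatment period".

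**The concern.** Two separate parts of the safety analysis are affected.

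The first is secondary. The severity tables are the main description of tolerability beyond the serious events. If they stop with the last dose, grades reached during the 25 days of safety follow-up are collected and then left out, including those that come from the planned laboratory visits.

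The second is primary. Safety is the first primary objective, and a single event separates an arm that continues from one that is closed. If two readers of the same protocol can disagree on whether a serious event is a SADR, the Step 1 result is not fully determined by the data. An event that could be due either to drug or to disease is where they would disagree.

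**Working it through.** **1. Grading window against collection window.** Inputs: 5 treatment days (Study Design) and 25 days of safety follow-up (recording period section).

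Share of the post-first-dose window that is graded = 5 / (5 + 25) = 5/30 = 17%.

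Scheduled post-baseline bloods fall on Days 7, 14 and 30, and none on Days 1 to 5, so none of them lies inside the graded window. The same analysis section names blood test alterations during treatment as a rare outcome for Fisher's test. Read literally, only bloods from unscheduled visits or local routine could supply it.

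**2. Does this limit reach the primary result?** The primary outcome list, Step 1 and Analysis of the primary outcome all refer to SADRs and contain no during-treatment limit. The summary of patients with any SAE contains none either. The limit applies to worst-grade summaries only.

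**3. Causality passages side by side.**

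| Passage | Test | Whose view |
|---|---|---|
| Table 3, adverse reaction | cannot be ruled out | reporter or Sponsor |
| Table 3, serious adverse reaction | reasonable probability | reporting investigator |
| Relationship to study agents (AE/SAE) | reasonable possibility | site investigator |

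Table 5 has separate categories Probable and Possible, the latter for events that disease or other drugs could also explain. A serious event rated Possible meets the first and third tests. On a natural reading it fails the second. An event that only the Sponsor considers related meets the first alone.

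**4. The plan's own Step 1 figures.** The plan states a type I error of 10% at a true rate of 30%, and power of 80% at 5%. The probability of passing is

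P(X ≤ c) = Σ C(20, x) p^x (1 − p)^(20 − x), summed over x = 0 to c.

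- c = 4: 0.2375 at p = 0.30 and 0.997 at p = 0.05.
- c = 3: 0.107 at p = 0.30 and 0.984 at p = 0.05.

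The stated 10% and 80% do not reproduce at 4 or fewer. The note under Primary outcomes uses less than 4, which is c = 3. Both are separate defects. They matter here only because they fix the baseline, so both cut-offs are shown.

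**5. Effect of uncounted SADRs.** The documents give no misclassification rate. Assume that a fraction q of patients with a SADR is not counted, independently, at the plan's null rate of 30%. The effective rate is 0.30 × (1 − q).

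| q | Effective rate | P(pass), ≤4/20 | P(pass), ≤3/20 |
|---|---|---|---|
| 0 | 0.30 | 23.8% | 10.7% |
| 10% | 0.27 | 33.8% | 17.0% |
| 20% | 0.24 | 45.6% | 25.7% |
| 30% | 0.21 | 58.6% | 36.9% |

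**6. SAE windows.** Last dose on Day 5 plus 25 days gives Day 30, which is also the last visit. The consent-to-last-visit sentence therefore agrees with the recording period. The treatment-period sentence does not.

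**The case against.** **The grading sentence is secondary, and may be loosely worded.** The first half stands. A reader might infer from the sentence that SADRs after Day 5 are not counted in Step 1. The documents do not support that: the SADR count has no such limit, and the absence of a stated SADR window is something an SAP commonly settles. Loose wording is a weaker defence, because the recording section itself separates the treatment period from the safety follow-up. It is also true that daily telephone contact runs to Day 5, so early symptoms are well covered. Laboratory grades are not.

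**Exposure.** One might add that most of the high-exposure period lies outside the graded window. That overstates it. With five equal daily doses and mono-exponential decline, the share of exposure after 120 h is (1/5) Σ exp(−ln 2 × 24j / t½), j = 1 to 5. This is 30% at the 35 h half-life in the Introduction and 13% at the 18 h in Appendix 1. The point does not rest on exposure.

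**The stricter test for serious reactions is not settled.** This stands. Step 1 refers to the whole definitions section, not to one table row. The text definitions of adverse drug reaction and serious reaction add no higher test, the site instruction uses the lower one, and Table 5 assigns no category to either row. The defect is an unresolved conflict, not a fixed higher bar.

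**Disputed ratings may be rare.** This also stands. Manifestations of COVID-19 progression are not recorded as AEs, and deaths clearly due to it are not reported as SAEs. Nothing in the protocol shows that Possible will be a common rating.

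**The SAE reporting sentence loses no data.** Largely correct: the same electronic SAE form alerts the safety desk, and recording runs to 25 days after the last dose. It remains a contradiction in the text, but a minor one.

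**Conclusion.** The point holds in three parts of unequal weight.

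(a) The secondary severity tables, read literally, cover about 17% of the collection window after first dose and exclude every scheduled post-baseline laboratory result. This follows directly from the text and needs no assumption beyond the literal reading.

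(b) The Step 1 endpoint rests on a term that the cited section does not itself define, with conflicting causality tests around it. The size is conditional. At a true rate of 30%, with 10% to 30% of SADRs uncounted, the chance of passing at 4 or fewer in 20 rises from 23.8% to 33.8%–58.6% (from 10.7% to 17.0%–36.9% at 3 or fewer). The uncounted fraction is an assumption. At a true rate near 5% the ambiguity hardly matters, since an arm passes 99.7% of the time even with full counting.

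(c) The two SAE reporting windows contradict each other, with little practical effect.

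The documents do not support the claim that the during-treatment limit removes events from the primary safety result.

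**What to change.** (a) In Analysis of the secondary outcomes, replace the treatment limit with a window from first dose to 25 days after the last dose, and treat the phrase on blood test alterations in the same way. The data are already collected. The price is AE tables that may look slightly less favourable.

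(b) Reconcile Table 3's serious adverse reaction row with its adverse reaction row and with Relationship to study agents. Then define SADR once, stating which Table 5 categories count and whose assessment counts, and have Step 1 and the primary outcome list refer to that definition. Which categories to include, and how to treat unassessable events, is for the sponsor to decide. It should be fixed before Step 1 is read, because it determines what can close an arm. This does not require Step 1 to wait for the full 25-day follow-up of the last of the 60 patients.

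(c) In the SAE reporting section, state one window for the Sponsor and the safety desk, consistent with the recording period.

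All three are changes of wording and add no data collection.

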## **STUDY PROCEDURES**

### ***Baseline***

Suitable subjects will be identified through laboratory diagnosis of SARS-CoV-2 infection according to the reference standard (molecular) method of each participating site. Eligible patients will be directly asked (if still present at hospital at the moment of the positive test result) or by phone interview (if at home) their consent for study entry. The following procedures will be completed and recorded in each patient eCRF:

- Confirmation of eligibility
- Explanation of the study protocol according to the patient information sheet and request for consent to the patient
- Acquisition of Informed Consent for: participation to the study; use of personal data; donation of biological samples for study purpose.
- Demographics (i.e. age, gender, weight, height)
- Disease history, including information on concomitant medications
- Clinical assessment (by direct observation if recruited on site or by phone interview if recruited at home)

Once the inclusion and exclusion criteria are confirmed patients will be assigned to the control or intervention arms, according to the random selection.

The Investigators should register in the Subject Screening Log the age and the microbiology results for SARS-CoV-2 of all the patients who are asked to enter the study, irrespective of their subsequent enrolment. If the patient is not subsequently enrolled, the reason will be indicated in the form.

